3.0 Study Design and Population

This is a prospective, single center study from the Ochsner Medical Center. We seek to enroll a total of 85 paid volunteers that collectively encompass the range of physiology seen in routine practice. For simplicity sake, the range can be broken down into 3 distinct groups: 1) healthy volunteers without cardiac risk factors or chronic medical conditions (“normal”) 2) clinical patients with cardiac risk factors and/or history of clinical coronary artery disease (CAD), percutaneous coronary intervention (PCI) or coronary artery bypass grafting (CABG) (“clinical”) 3) patients with large myocardial infarctions demonstrated on prior PET stress testing (“infarct”). Volunteers will be recruited by “word-of-mouth” and through electronic records chart review. “Normal” volunteers will be consented and screened by history and laboratory tests for unrecognized cardiovascular risk factors, nicotine and caffeine. “Clinical” and “infarct” volunteers will not require laboratory tests other than caffeine levels. Once screened and consented, volunteers will undergo dipyridamole myocardial perfusion 3-D PET/CT stress testing with variable Rb-82 infusion profiles per the attached protocol. Female volunteers will also be questioned on their menstrual history and undergo urine pregnancy testing if appropriate on the day of the scan. The first 5 volunteers will be not be used in the final analysis but will be used to confirm proper scanner function, reconstruction settings and appropriate filter settings.

4.0 Inclusion/Exclusion Criteria

Normal Volunteers

The normal population will include 40 volunteers (20 men and 20 women).

Inclusion Criteria:

- Adults ≥ 18 and < 40 years old able to give informed consent.
- Ability to abstain from caffeine for 48 hours

Exclusion Criteria:

- Any chronic cardiac disease or condition (e.g., hypertension, hyperlipidemia)
- Any chronic systemic disease or condition (e.g., diabetes, systemic lupus, rheumatoid arthritis)
- Tobacco use
- Family history in a first degree relative with clinical CAD (h/o PCI, MI or CABG) in men < 55 or women < 65
- Severe claustrophobia
- Positive urine pregnancy test
- Inability to give informed consent
- BMI ≥ 30 or BMI > 25 and < 30 provided waist to hip ratio > 0.80 in women or 0.90 in men.

“Clinical” Volunteers

The “clinical” population will include 20 volunteers.

Inclusion Criteria:

- Adults ≥ 18 years old able to give informed consent.
- Any cardiac risk factor including hypertension, hyperlipidemia, diabetes mellitus or tobacco use OR
- CAD defined by with history of PCI or CABG, Coronary Ca score > 400 , or dense coronary calcifications noted on chest CT
- Ability to abstain from caffeine for 48 hours

Exclusion Criteria:

- Severe claustrophobia
- Hemodynamic instability or unstable symptoms
- Positive urine pregnancy test
- Inability to give informed consent

“Infarct” Volunteers

The “infarct” population will include 20 volunteers.

Inclusion Criteria:

- Adults ≥ 18 years old able to give informed consent.
- Prior cardiac PET scan demonstrating a fixed defect $\geq 15\%$ of the LV myocardium with relative uptake $\leq 60\%$ maximum uptake.
- In addition, to the perfusion defect, each volunteer requires either:
 - FDG PET or MRI viability studies confirming infarct OR
 - akinesis and wall thinning on ECHO within the same territory as the PET defect in addition to Q-waves on ECG
- Ability to abstain from caffeine for 48 hours

Exclusion Criteria:

- Severe claustrophobia
- Hemodynamic instability or unstable symptoms
- Positive urine pregnancy test
- Inability to give informed consent

5.0 Study Procedures

All “normal” participants eligible for inclusion will have initial screening by research staff and/or research physicians. Initial screening will consist of an assessment of the volunteer’s medical history, a manual blood pressure (BP) measurements, height and weight measurements and when appropriate waist to hip ratio, and venipuncture for fasting lipids, basic metabolic profile and nicotine. If the “normal” volunteer has results for any of the required laboratory testing within the past 90 days, venipuncture will not be required. Informed consent will be obtained if venipuncture is required. Exclusion from the study will result if the “normal” volunteer:

[figure not shown]
- is noted to have any chronic systemic medical condition on interview
- has a manual SBP \geq 130 or DBP \geq 80.
- Has an “abnormal” lipid profile. A “normal” lipid profile is defined as a total cholesterol \leq 200 and LDL \leq 130 and TG \leq 200 and HDL \geq 40. Volunteers with values outside of these defined norms will be deemed “abnormal”
- has detectible nicotine levels.
- BMI $>$ 30 OR BMI $>$ 25 and $<$ 30 with waist-to-hip ratio $>$ 0.9 in men and $>$ 0.80 in women

If the “normal” volunteer is excluded based on results of the initial screen, she/he could meet inclusion criteria for “clinical”. If the “normal” volunteer is not excluded based on results of the initial screen, informed consent for participation in the research study in addition to consent for the research PET scan will be obtained. Once informed consent is obtained the patient will be scheduled for the research PET scan. On the day of the PET scan and as part of the PET scan protocol, IV access will be placed. At that time, a blood sample will be obtained and sent for caffeine levels. Female volunteers will also undergo urine pregnancy testing on the day of the scan. If the pregnancy test is positive, the patient will be excluded. The volunteer will then undergo pharmacologic PET stress testing per the attached protocol using a standard weight-based dosing of dipyridamole. Once the PET stress scan is completed, the volunteer’s participation is completed.

All “clinical” and “infarct” participants eligible for inclusion will have initial screening by research staff and/or research physicians. Initial screening will consist of an assessment of the volunteer’s medical history and prior PET studies (infarcts). If the “clinical” or “infarct” volunteer is not excluded based on results of the initial screen, informed consent for participation in the research study in addition to consent for the research PET scan will be obtained. Once informed consent is obtained the patient will be scheduled for the research PET scan. On the day of the PET scan and as part of the PET scan protocol, IV access will be placed. At that time, a blood sample will be obtained and sent for caffeine levels. Female volunteers will also undergo urine pregnancy test (if appropriate) on the day of the scan. If the pregnancy test is positive, the patient will be excluded. The volunteer will then undergo pharmacologic PET stress testing per the attached protocol using a standard weight-based dosing of dipyridamole. Once the PET stress scan is completed, the volunteer’s participation is completed.

PROTOCOL

(n=85, 40 normal (20♂, 20♀), 45 clinical patients (20 CAD/risk factor patients and 20 large infarcts))

- Rb-82 dose = 0.31mCi/kg, max dose =30mCi per injection
- Total Rb-82 dose is 75-125 mCi/all scans
- * - If dose of 0.31mCi/kg causes saturation of camera, the resting scan will be repeated at a lower dose of 0.25mCi/kg

Scan time = ~ 32 minutes

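### The protocol box itemises its 45 patients as 20 + 20 = 40, and the five unanalysed run-in volunteers are defined only by enrolment order, so neither group quotas nor activity coverage is secured

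*Combined protocol and SAP*

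**What the plan says.** **Enrolment and run-in (Section 3.0).** The plan says "We seek to enroll a total of 85 paid volunteers" and then "The first 5 volunteers will be not be used in the final analysis". Those five "will be used to confirm proper scanner function, reconstruction settings and appropriate filter settings". They are identified by order of enrolment alone; no group, sex, body weight or activity level is required.

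**Group sizes (Section 4.0).** "The normal population will include 40 volunteers (20 men and 20 women"; "The “clinical” population will include 20 volunteers"; "The “infarct” population will include 20 volunteers". The section does not say whether these are numbers enrolled or numbers analysed.

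**Protocol box (end of Section 5.0).** The total is 85, made up of 40 normal volunteers and "45 clinical patients (20 CAD/risk factor patients and 20 large infarcts". Rb-82 activity is 0.31 mCi/kg with a maximum of 30 mCi per injection, and the total over all scans is 75-125 mCi. If the camera saturates, the resting scan is repeated at a lower weight-based activity.

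**Number of scans (Section 7.0).** Each volunteer contributes three resting and two stress values.

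**Saturation (Section 1.0).** The background explains that high early count rates can saturate the detectors, that each 3D camera has a suitable range of administered activity, and that scatter and random events are more frequent at higher activity.

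**The concern.** Two separate matters meet in the run-in.

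The first is a head count. The box's patient subtotal does not equal its parts, and the five volunteers left over are not named. The box puts them among the patients, while Section 3.0 could take them from any group. If quotas are filled from the box as printed, the number analysed in each group depends on who enrols first. Section 2.0 plans a separate comparison with published flow ranges for each of the three groups, so the group counts have a use.

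The second is coverage, and it would remain if the box were corrected. The run-in exists to check the scanner, the reconstruction and the filters. By the protocol's own account, saturation depends on administered activity, and activity rises with body weight. Five volunteers taken in order of arrival may not include anyone near the top of that range. A problem at high activity could then first appear in the analysed sample.

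**Working it through.** **1. Head count**

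- Box total: 40 + 45 = 85, which agrees with Section 3.0.
- Box patient subtotal: 20 + 20 = 40, against 45 stated. The gap is 5.
- Section 4.0: 40 + 20 + 20 = 80.
- Enrolled less itemised: 85 − 80 = 5, exactly the size of the run-in.

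So 85 = 5 run-in + 40 + 20 + 20 accounts for every figure except the placing of the five under patients.

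**2. Numbers analysed if the five come out of a group quota**

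- All five are normals counted in the 40: 40 − 5 = 35, a loss of 5/40 = 12.5%. Standard errors that scale with 1/√n grow by √(40/35) = 1.069, about 7%.
- All five come from one patient group counted in its 20: 20 − 5 = 15, a loss of 5/20 = 25%. The factor is √(20/15) = 1.155, about 15%.

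The plan gives no sample-size calculation, so these cannot be compared with a power target.

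**3. Activity reached in the run-in**

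- Weight at which the cap applies: 30/0.31 = 96.8 kg.
- Normal volunteers must have a BMI below 30 under Section 4.0. Height needed to weigh 96.8 kg at that limit: √(96.8/30) = 1.80 m. At a BMI of 25: √(96.8/25) = 1.97 m.
- A normal volunteer of 1.70 m weighs less than 30 × 1.70² = 86.7 kg and receives less than 0.31 × 86.7 = 26.9 mCi.
- A normal volunteer of 1.80 m at a BMI of 25 weighs 81.0 kg and receives 25.1 mCi (84% of the cap). Just under a BMI of 30, the same volunteer receives about 30 mCi.

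The documents give no weight distribution. Let p be the assumed share of volunteers at or above 96.8 kg, and treat the first five as independent draws. The chance that none reaches the cap is (1 − p)^5:

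| Assumed p | Chance that none of five reaches the cap |
|---|---|
| 5% | 0.95^5 = 77% |
| 10% | 0.90^5 = 59% |
| 20% | 0.80^5 = 33% |
| 30% | 0.70^5 = 17% |

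**4. Cap against total activity**

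- Five injections (three rest, two stress) at the cap: 5 × 30 = 150 mCi, above the stated upper total of 125 mCi.
- 125/5 = 25 mCi per injection, which 0.31 mCi/kg reaches at 25/0.31 = 80.6 kg.

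The two figures in the box therefore conflict for heavier volunteers.

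**The case against.** The strongest reply is that the counts reconcile. If the 40, 20 and 20 already included the run-in, enrolment would be 80, so a total of 85 points to five extra volunteers. This stands. A reader might infer that the plan intends to analyse only 35 normals. The documents do not support that; the loss is a risk from unclear wording.

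Next, the stated hypotheses concern within-person variation of whole-heart flow, and Section 3.0 presents the three groups as a simplification. No power target or sex comparison depends on an exact group size. This also stands, and it limits the importance of losing five from a group.

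On activity, three points stand in part.

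- The box has its own response to saturation. However, that response names only the resting scan and acts only once saturation has happened.
- Activity is not the only influence. Section 1.0 says the low-flow profile was developed partly to limit saturation, and the crossover gives each volunteer both profiles. Lighter run-in volunteers would still exercise the bolus and the low-count end of the range, provided they follow the same scan sequence.
- A reader might infer that the first five will be lean normals of about 60-70 kg, receiving 18.6-21.7 mCi (62-72% of the cap). No weights are given, Section 4.0 admits some volunteers with a BMI between 25 and 30, and a tall normal volunteer can reach the cap. That scenario is one low case.

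Finally, a reader might infer that settings are locked after the fifth volunteer, or that an infarct heart needs its own settings. Neither is stated. Section 3.0 speaks only of confirming settings.

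**Conclusion.** The point holds, at minor severity. The box's patient subtotal is wrong by five, and the run-in is neither labelled nor tied to a group. The most natural reading preserves 40, 20 and 20 for analysis. The literal one could leave 35 of 40 normals or 15 of 20 in a patient group.

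The coverage gap is a separate matter and does not follow from the miscount. It rests on the first-five rule, the weight-based activity and the protocol's own account of saturation. Its size depends on a weight distribution that the documents do not give: a 77% to 17% chance of missing the cap if 5% to 30% of volunteers are heavy enough. Nothing in the documents shows that saturation will occur, or that the run-in will in fact miss the upper range.

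The conflict between the 30 mCi per-injection cap over five injections and the 75-125 mCi total is in the text as it stands. It must be reconciled before a heavier run-in volunteer is scheduled.

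**What to change.** 1. Restate the box as 85 = 5 run-in (not analysed) + 40 normal + 20 clinical + 20 infarct. Say in Sections 3.0 and 4.0 that group and sex quotas are counted after the run-in. This costs only wording.
2. Have the sponsor reconcile the per-injection cap with the total activity over five injections before step 3. No dose is proposed here.
3. Replace selection by order alone with a run-in of five, scheduled from volunteers already planned, that spans low to high body weight. Including one volunteer from each group is optional.
4. State that reconstruction and filter settings are fixed before volunteer 6 is scanned.

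Steps 3 and 4 add no volunteers or scans. The downside is a short wait until a heavier volunteer can be scheduled, within a recruitment period that Section 12.0 puts at about six weeks.

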phases of the acquisition, the activity is distributed widely throughout the body tissues, and only a small fraction of the administered activity resides within the heart and adjacent organs in the scanner field of view. Furthermore, for short-lived tracers such as ^{82}Rb , the isotope activity will decay several half-lives over the course of imaging. Consequently, late-phase count rates (perfusion images) can be orders of magnitude lower than those of the early-phase, risking low-quality perfusion images that are noisy and require the use of smoothing filters at the expense of spatial resolution and image contrast(10). Therefore, for each 3D camera, there is an ideal range of administered Rb-82 activity such that detector saturation is avoided, and perfusion images are diagnostic(11).

Furthermore, during 3D acquisition, there is significant scatter and random detections that are corrected for within the sub-processing systems. These events occur much more frequently with higher activities and are non-linear with decay. Hence, with short lived tracers such as Rb-82, the scatter and random corrections must occur at short intervals (5-10 seconds) and images created from the summed scatter and random corrected intervals(12). The necessary processes to achieve accurate and diagnostic images requires a tremendous amount of computational power and time.

Reconstruction times on first generation 3D PET/CT could take ~45 minutes per dataset when using 5 second intervals. Therefore, a 3/9/22 Rb-82 infusion profile (20mls/min) was developed: 1) to mitigate scatter and the lengthy processing time 2) to mitigate detector saturation 3) to maintain diagnostic quality perfusion images 4) to obtain accurate MBF data. However, on modern day 3D PET/CT scanners with faster internal components and improved processing speeds, the necessity of the low flow profile vs. the standard profile (50mls/min bolus) is under debate. We seek to test these profiles on 3 distinct populations of volunteers.

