7.0 Statistical Analysis

This is a measurement reliability study in a 2x2 factorial design. Study factors are infusion flow rate (20 or 50) at rest and stress. The linear nature of data acquisition takes about 45 minutes and yields five absolute values for each subject: three resting values and 2 stress values. The first 2 resting values and the 2 stress values condition are obtained in a cross-over fashion by infusion flow rate (infusion level assigned randomly for first resting scan and for first stress scan). The third resting value will be obtained at either a 20 or 50 infusion flow rate and will be used to determine precision (test-retest variability) against the same infusion profile obtained in the first two infusions.

Precision and variability will be determined for global, average quadrant, and individual pixel values of rest flow, stress flow and CFR. Standard summary statistical tests will be used. Applicable tests are 2-tailed, and $p < 0.05$ will be considered statistically significant. Linear regression will be reported between rest perfusion and rest pressure rate product (PRP). Paired or unpaired Student *t* test will be used to evaluate continuous variables where appropriate. The Pitman-Morgan *F* test will be used to test for differences in variability of perfusion between groups. To compare the histogram distribution between groups of stress perfusion and CFR for each of 1344 pixels as percentage of LV in color-

coded ranges of coronary flow capacity, we will use the Kolmogorov-Smirnov (KS) test for differences in histogram distribution.

8.0 Reporting of Adverse Events or Unanticipated Problems involving Risk to Participants or Others

Adverse events or unanticipated problems will be reported to [name] or [name] at [contact] and the Internal Review Board as directed by Ochsner Medical Center IRB rules and regulations.

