9.0 Radiation Risks

Participants who enroll in the study will receive ionizing radiation. The effective dose of a cardiac PET scan is approximately 6.2mSV or less. This is about 12% of the occupational exposure allowed for a radiation worker. This is also about twice the annual amount of natural background radiation exposure.

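### The stated Rb-82 total of 75-125 mCi does not cover the plan's own dosing rule, which gives up to 150 mCi over five scans

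*Combined protocol and SAP*

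**What the plan says.** The PROTOCOL box at the end of section 5.0 holds three statements on administered activity:

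- the rule for each injection: "Rb-82 dose = 0.31mCi/kg, max dose =30mCi per injection";
- the total per participant: "Total Rb-82 dose is 75-125 mCi/all scans";
- a contingency, marked with an asterisk: "If dose of 0.31mCi/kg causes saturation of camera, the resting scan will be repeated at a lower dose of 0.25mCi/kg".

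Section 7.0 fixes the number of scans, saying that the acquisition "yields five absolute values for each subject: three resting values and 2 stress values".

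Section 4.0 sets no limit on weight in kilograms for any group. The clinical and infarct groups have no BMI limit either. Normal volunteers are excluded at a BMI of 30 or more, or with "BMI > 25 and < 30 provided waist to hip ratio > 0.80 in women or 0.90 in men", so a BMI between 25 and 30 is allowed when the waist-to-hip ratio is acceptable.

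Section 9.0 gives the radiation exposure: "The effective dose of a cardiac PET scan is approximately 6.2mSV or less". It does not name the activity for which that figure was computed.

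**The concern.** The total is given without qualification: it is not called typical, expected or maximal. It should therefore agree with the number of scans multiplied by the dose per scan. The two ends of the range, divided by five, are 15 and 25 mCi per injection, yet the line above allows 30 mCi. Staff who follow the per-injection rule will exceed the stated total for heavier participants, and nothing in the eligibility criteria keeps those participants out.

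This is the plan's only statement of total administered activity, and it applies to paid volunteers, 40 of whom are healthy. What is at stake is the accuracy of the exposure statement.

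**Working it through.** **Inputs.** Dose 0.31 mCi/kg, cap 30 mCi per injection, stated total 75-125 mCi, repeat dose 0.25 mCi/kg (all from the PROTOCOL box, section 5.0); five scans, three rest and two stress (section 7.0). The scan diagram is not shown in the text available, so the count of five rests on section 7.0.

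**Can the stated range be reproduced?** With weight w in kg and no repeat, total = 5 × min(30, 0.31w), which is 1.55w below the cap.

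- Lower end: 75 / 1.55 = 48.4 kg (15 mCi per injection).
- Upper end: 125 / 1.55 = 80.6 kg (25 mCi per injection).
- The cap binds at 30 / 0.31 = 96.8 kg, and the total is then 5 × 30 = 150 mCi; 150 / 125 = 1.20.

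The range is therefore reproduced for about 48.4 to 80.6 kg, but not as the full span of the rule. A different number of scans does not rescue it. Three or four injections would stay below 125 mCi at the cap (90 and 120 mCi), but both contradict section 7.0.

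**With one rest scan repeated for saturation.** This adds a sixth injection. The plan does not say whether only the repeat uses 0.25 mCi/kg or whether all later scans do, so both are shown. The second reading takes the saturated scan to be the first.

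- Only the repeat: 5 × min(30, 0.31w) + min(30, 0.25w). Below the cap this is 1.55w + 0.25w = 1.80w, and 125 mCi is passed at 125 / 1.80 = 69.4 kg.
- All later scans: min(30, 0.31w) + 5 × min(30, 0.25w). Below the cap this is 0.31w + 1.25w = 1.56w, and 125 mCi is passed at 125 / 1.56 = 80.1 kg.
- At 0.25 mCi/kg the 30 mCi cap is reached at 30 / 0.25 = 120 kg, so both readings have the ceiling 6 × 30 = 180 mCi; 180 / 125 = 1.44.

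| Weight (kg) | Five scans (mCi) | Six, only the repeat at 0.25 (mCi) | Six, all later at 0.25 (mCi) |
|---|---|---|---|
| 45 | 69.8 | 81.0 | 70.2 |
| 70 | 108.5 | 126.0 | 109.2 |
| 80.6 | 124.9 | 145.1 | 125.7 |
| 90 | 139.5 | 162.0 | 140.4 |
| 96.8 | 150.0 | 174.2 | 151.0 |
| 100 | 150.0 | 175.0 | 155.0 |
| 119 | 150.0 | 179.8 | 178.8 |
| 120 or more | 150.0 | 180.0 | 180.0 |

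**Are such weights eligible?** Yes, in every group. At a height of 1.80 m, BMI 25 is 25 × 1.80² = 81.0 kg and BMI 30 is 97.2 kg, so even the normal group can include people above 80.6 kg.

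**The case against.** The five-scan arithmetic is not in dispute. The case on the other side concerns how far it reaches.

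- **The line may be a usual range or a limit.** If it is a usual range, heavier participants exceeding it shows loose wording, not a dosing error. If 125 mCi is a study limit that applies alongside the 30 mCi cap, simply restating the total upward would relax that limit. This objection stands. The text does not settle the matter, so the fix has to cover both readings. Neither reading makes the line adequate as it is: under the first it lacks a maximum, and under the second it conflicts with the cap.
- **The sixth injection is contingent.** A reader might infer that participants will receive 180 mCi. The documents do not support that. The repeat happens only on saturation, for which no frequency is given. The ceiling is reached exactly only from 120 kg, where the repeat is no longer a lower dose because both injections meet the 30 mCi cap. The trigger is worded for 0.31 mCi/kg, a rate not given above 96.8 kg, so applying it there is an inference. The scan to which the asterisk attaches cannot be seen. Section 3.0 also uses the first five volunteers to confirm scanner function, so saturation might mainly concern them. The figure is therefore a theoretical ceiling, and the main result is 150 mCi.
- **Section 9.0 is not shown to be wrong.** A reader might infer that the effective dose is understated by the same 20%. The documents give no mSv-per-mCi factor and do not tie 6.2 mSv to 75-125 mCi, so that inference has no basis. The figure may already allow for the maximum.

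**Conclusion.** The stated total is inconsistent with the dosing rule beside it. Without a repeat, the rule gives 75-125 mCi only for about 48.4 to 80.6 kg, and it reaches 150 mCi from 96.8 kg, 25 mCi or 20% above the stated upper end. One repeated rest scan lowers the weight at which 125 mCi is passed to about 69.4 kg (only the repeat at 0.25 mCi/kg) or 80.1 kg (all later scans at 0.25 mCi/kg), with totals approaching 180 mCi near 120 kg.

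This rests on five scans per participant as in section 7.0, on the per-injection rule being followed as written, and, for the six-injection figures, on one repeat under the same 30 mCi cap. The documents give no weight distribution, so the share of participants affected is unknown.

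It is a minor correction to the exposure statement. The per-injection rule is not shown to be wrong, and the discrepancy does not touch the hypotheses, sample size or analysis.

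**What to change.** State which rule governs.

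- **If the per-injection rule governs:** give the total as up to 150 mCi for five scans, plus up to 30 mCi for one repeated rest scan, and keep 75-125 mCi as the usual range for about 48-81 kg. The cost is wording and a less favourable stated maximum. Dosing and image counts do not change.
- **If 125 mCi is a limit:** say so, lower the per-injection cap to 125 / 5 = 25 mCi, and count any repeat within the limit. For example, if a first rest injection of 25 mCi saturates the camera, 100 mCi remains for five injections, or 20 mCi each. This does change dosing. Participants above 80.6 kg would receive less activity, by up to 5 mCi of 30 mCi per injection, when section 1.0 already warns that "late-phase count rates (perfusion images) can be orders of magnitude lower than those of the early-phase, risking low-quality perfusion images".

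In either case, say whether the 0.25 mCi/kg dose applies to the repeat alone or to all later scans. Confirm that the section 9.0 effective dose was computed for the governing maximum, and restate it only if it was not.
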